Data Monitoring Committee (DMC)	The DMC, an independent committee of experts in cardiovascular disease plus one biostatistician, will review trial safety and provide guidance consistent with the objectives of the study and appropriate ethical requirements. The DMC charter will be developed in collaboration with the DMC members and will be finalized before the first patient is randomized.
Cardiopulmonary Exercise Test (CPET) Core Lab	The independent central CPET Core Lab will qualify CPET at each study site. In addition, CPET data for eligibility and efficacy analyses will be reviewed centrally by the CPET Core Lab. Procedural details will be documented in a CPET Core Lab manual.
Echocardiography Core Lab	The independent central Echocardiography Core Lab will be blinded to treatment assignment and will review echocardiography data for efficacy analyses. Procedural details will be documented in an Echocardiography Core Lab manual.
Clinical Events Adjudicator(s)	Blinded adjudication of hospitalizations of cardiovascular etiology and all deaths will be performed by the independent Clinical Event Adjudicator(s). The adjudicator(s) will be provided with all relevant documentation related to each event. The procedures will be described in an adjudication document. Adjudication results will be the basis for the final analysis.

TABLE OF CONTENTS

KEY STUDY ROLES	2
TABLE OF CONTENTS.....	4
SPONSOR SIGNATURE.....	11
INVESTIGATOR'S SIGNATURE	12
LIST OF ABBREVIATIONS AND DEFINITIONS OF TERMS.....	13
SYNOPSIS.....	16
ELIGIBILITY CRITERIA.....	19
INCLUSION CRITERIA.....	19
EXCLUSION CRITERIA	21
SCHEDULE OF EVENTS	24
1. INTRODUCTION	27
1.1 HEART FAILURE WITH PRESERVED EJECTION FRACTION	27
1.2 PATHOPHYSIOLOGY OF HFPEF.....	27
1.3 RATIONALE FOR USE OF AN SGC STIMULATOR IN HFPEF.....	28
1.3.1 IW-1973	29
1.3.1.1 Nonclinical Data in Support of Clinical HFpEF Investigations	29
2. STUDY OBJECTIVES.....	30
3. INVESTIGATIONAL PLAN.....	31
3.1 OVERALL STUDY DESIGN AND PLAN.....	31
3.2 DISCUSSION OF STUDY DESIGN AND CONTROL GROUP.....	33
3.3 STUDY DURATION	34
3.4 STUDY POPULATION	34
3.4.1 Removal of Patients from Therapy or Assessment.....	34
3.4.2 Early Termination Procedures	35
3.5 STUDY TREATMENT(S)	36
3.5.1 Description of Treatment(s).....	36
3.5.1.1 Investigational Product	36
3.5.1.2 Placebo	36
3.5.1.3 Packaging and Labeling.....	36
3.5.1.4 Dosage.....	36
3.5.1.5 Storage and Accountability.....	37
3.5.2 Method of Assigning Patients to Treatment Groups.....	38

NT-proBNP	N-terminal pro B-type natriuretic peptide
NYHA	New York Heart Association
pd	postdose
PDE	phosphodiesterase
PK	pharmacokinetic(s)
PT	preferred term
QD	once daily (1×/day)
QOL	quality of life
RBC	red blood cell
RDW	red blood cell distribution width
RER	respiratory exchange ratio
RR	respiratory rate
SAE	serious adverse event
SAP	statistical analysis plan
sGC	soluble guanylate cyclase
SOC	system organ class
TEAE	treatment-emergent adverse event
UACR	urine albumin creatinine ratio
UGT	uridine diphosphate–glucuronosyl transferase
ULN	upper limit of normal
US	United States

SYNOPSIS

Sponsor
Ironwood Pharmaceuticals, Inc.
Name of Finished Product
IW-1973 Tablet (pralicipat)
Name of Active Ingredient
IW-1973
Study Title
A Multicenter, Randomized, Double-blind, Placebo-controlled, Phase 2 Study Evaluating the Safety and Efficacy of Different Doses of IW-1973 over 12 Weeks in Patients with Heart Failure with Preserved Ejection Fraction (CAPACITY HFpEF)
Study Number
C1973-204
Study Phase: 2
Study Objectives
Primary

• To assess the safety of oral IW-1973 when administered for approximately 12 weeks to patients with heart failure with preserved ejection fraction (HFpEF)• To evaluate effect of oral IW-1973 on peak exercise capacity when administered for approximately 12 weeks to patients with HFpEF, both in all patients and in patients without permanent or persistent atrial fibrillation
Secondary

• To evaluate the effect of oral IW-1973 on exercise and functional capacity when administered for approximately 12 weeks to patients with HFpEF
Study Design
This Phase 2, multicenter, randomized, double-blind, placebo-controlled, parallel-group study will evaluate the safety and efficacy of IW-1973 compared with placebo when administered daily for approximately 12 weeks (2 weeks of twice-daily [BID] dosing followed by 10 weeks of once-daily [QD] dosing) in the indicated patient population. At the Day 1 Visit, eligible patients will be stratified by atrial fibrillation status and by baseline peak VO ₂ (<60% or ≥60% of age- and sex-adjusted normal values and with respiratory exchange ratio [RER] ≥1.0 as determined by cardiopulmonary exercise test [CPET]). Patients will be randomized in a 1:1 ratio to daily 40 mg IW-1973 or placebo (see Study Treatment below). All patients will receive their first morning BID dose in the clinic on Day 1 and their first QD dose at the Week 2 Visit (Day 15 [±3]); for these 2 visits, patients must stay in the clinic for approximately 4 hours postdose and will be released at the Investigator's discretion

after undergoing safety, efficacy, and pharmacokinetic (PK) assessments per the **Schedule of Events**. At the Week 4, Week 8, and End of Treatment visits, patients will again return to the clinic for study drug administration; for safety, efficacy, and PK assessments; and to receive additional study drug and other supplies, as applicable. Patients will return to the clinic 28 days (Day 113 \pm 7) after their last study drug dose for the final Follow-up Visit.

Study Treatment

Patients will receive study drug for up to 89 days.

For patients randomized via Protocol Amendment 2 (or earlier): On Day 1, patients will be randomized in a 1:1:1:1 ratio to the following 4 regimens:

Dose	Weeks 1 and 2, BID Dosing	Weeks 3 through 12, QD Dosing
10 mg	one 5-mg IW-1973 Tablet, orally twice daily	two 5-mg IW-1973 Tablets, orally once daily
20 mg	one 10-mg IW-1973 Tablet, orally twice daily	two 10-mg IW-1973 Tablets, orally once daily
40 mg	one 20-mg IW-1973 Tablet, orally twice daily	two 20-mg IW-1973 Tablets, orally once daily
Placebo	one matching placebo tablet, orally twice daily	two matching placebo tablets, orally once daily

BID=twice daily; QD=once daily

For patients randomized starting with Amendment 3 to the protocol: Patients will be randomized on Day 1 in a 1:1 ratio to the following 2 regimens:

Dose	Weeks 1 and 2, BID Dosing	Weeks 3 through 12, QD Dosing
40 mg	one 20-mg IW-1973 Tablet, orally twice daily	two 20-mg IW-1973 Tablets, orally once daily
Placebo	one matching placebo tablet, orally twice daily	two matching placebo tablets, orally once daily

BID=twice daily; QD=once daily

Study Population and Planned Number of Patients

The study will enroll approximately 184 adult patients with established heart failure and limited exercise capacity with ejection fraction of at least 40% and who have at least 2 of 4 risk factors for HFrEF (diabetes/prediabetes, hypertension, obesity, advanced age [\geq 70 years]). The number of patients admitted with permanent or persistent atrial fibrillation will be limited to approximately 36 in the study.

See [Eligibility Criteria](#) for full inclusion and exclusion criteria.

Study Assessments

Safety: Medical history, prior and concomitant medications and surgeries/procedures, and adverse events will be collected. Physical examination, vital sign measurements including orthostatic blood pressure, clinical laboratory tests, pregnancy tests, and electrocardiograms will be performed.

Efficacy: CPET, 6-minute walk tests (6MWT), and echocardiography will be performed. New York Heart Association (NYHA) functional classification will be determined. Cardiac events will be analyzed. Blood and urine will be collected for biomarker determinations.

Patient-reported outcomes: Patients will self-administer the following questionnaires: Kansas City Cardiomyopathy Questionnaire (KCCQ), Sheehan Disability Scale (SDS), EuroQol-5D-5L (EQ-5D-5L), and Quick Inventory of Depressive Symptomatology (QIDS)-SR-16.

Pharmacokinetics: Blood will be collected to determine plasma concentrations of IW-1973.

Dose Reduction, Individual Stopping Criteria, and Data Monitoring Committee (DMC)

Per Investigator discretion, a dose reduction for an individual patient is allowed after consultation with the Medical Monitor. If approved, the patient will reduce his or her daily dose by half, ie, from 2 to 1 tablet daily. It is recommended that the patient to be evaluated in the clinic in association with any dose modification. Each patient's dose may only be reduced once and will not be increased after reduction.

Also on an individual basis, a patient will be discontinued from study drug dosing if any of the following are reported: a study drug-related serious adverse event (SAE) of spontaneous bleeding; a life-threatening symptomatic hypotension-related SAE; or 2 study drug-related symptomatic hypotension-related SAEs.

An independent DMC will review trial safety data both periodically and on an ad hoc basis. After each periodic or ad hoc review of safety data, the DMC will recommend trial continuation, continuation with modification, or termination. Details will be provided in a DMC charter, which will be developed in collaboration with the DMC members and will be finalized before the first patient is randomized.

Statistical Methods

There will be no statistical adjustment for multiple testing. All reported p-values will be considered nominal. Ninety-two patients per arm will provide approximately 90% power to detect a clinically meaningful difference between the 40-mg IW-1973 treatment arm and the placebo treatment arm in change from baseline at Week 12 peak VO₂ in all patients and/or in patients without permanent or persistent atrial fibrillation.

Final Date: 27 June 2018

ELIGIBILITY CRITERIA

INCLUSION CRITERIA

Patients must meet all of the following criteria to be eligible for enrollment in this study:

1. Patient has signed an informed consent form (ICF) before any study-specific procedures are performed.
2. Patient is an ambulatory male or female ≥ 45 years old at the Screening Visit.
3. Patient has heart failure with ejection fraction (EF) of $\geq 40\%$ as assessed within 12 months of the Screening Visit, without previously documented EF of $<40\%$. (If echocardiography results are not documented in the patient's medical history, the Investigator may perform an echocardiography at the Screening Visit.) Eligibility will be based on Investigator analysis.
4. Patient has a peak VO₂ measuring $<80\%$ of age- and sex-adjusted normal (see table) and a respiratory exchange ratio (RER) ≥ 1.0 at the Baseline Visit cardiopulmonary exercise test (CPET) as determined by the CPET Core Lab.

Age- and Sex-adjusted Normal Peak VO₂

Age (years)	Sex	Normal Peak VO ₂ (mL O ₂ /kg/min)	80% of Normal Peak VO ₂ (mL O ₂ /kg/min)
50-59	M	36	28.8
50-59	F	29	23.2
60-69	M	33	26.4
60-69	F	27	21.6
>70	M	29	23.2
>70	F	27	21.6

Source: Fletcher et al, 1995 (1)

F=female; M=male

5. Patient may have permanent or persistent atrial fibrillation; total number of patients with permanent or persistent atrial fibrillation will be limited to approximately 36. (Note: Patients with intermittent [paroxysmal] atrial fibrillation must be in normal sinus rhythm at the time of the baseline CPET; these patients will not count toward the limit of 36 patients with permanent or persistent atrial fibrillation.)
6. Patient has evidence in medical history supporting clinical heart failure syndrome consisting of at least 1 of the following:
 - a. Hospitalization or emergency department visit for heart failure within the past year, with at least 2 of the following documented:
 - o Volume overload on presentation as evidenced by at least 2 of the following 5 signs: jugular venous distension, pitting edema $\geq 1+$, ascites, pulmonary congestion on chest x-ray, or pulmonary rales

- B-type natriuretic peptide (BNP) (≥ 100 [sinus rhythm], ≥ 200 pg/mL [atrial fibrillation]) or N-terminal pro BNP (NT-proBNP) (≥ 300 [sinus rhythm] or ≥ 600 pg/mL [atrial fibrillation])
 - Treatment with intravenous (IV) diuretics with clinical response
- b. BNP (≥ 100 [sinus rhythm], ≥ 200 pg/mL [atrial fibrillation]) or NT-proBNP (>300 [sinus rhythm], >600 pg/mL [atrial fibrillation]) within the past 6 months. (If needed for eligibility, a sample for NT-proBNP level may be collected at the Screening Visit.)
 - c. Echocardiographic evidence within the past 12 months of at least 2 of the following: left ventricular (LV) hypertrophy, left atrial (LA) enlargement, or diastolic dysfunction (medial E/e' ratio ≥ 15)
 - d. Hemodynamic evidence of elevated filling pressures, as indicated by pulmonary capillary wedge pressure ≥ 15 mmHg at rest or >25 mmHg with exercise within the past 12 months, or left ventricular end-diastolic pressure ≥ 15 mmHg
7. Patient has New York Heart Association (NYHA) Class II-IV symptomatology as assessed at the time of the Screening Visit. The classifications are described in Section 3.8.7 (Table 6).
 8. Patient is on stable dose(s) of any current cardiovascular medication (eg, angiotensin-converting enzyme [ACE] inhibitors, angiotensin receptor blockers [ARBs], beta-blockers, mineralocorticoid receptor antagonists [MRAs]) for at least 1 month before the Baseline and Randomization Visits with the regimen expected to remain unchanged for the duration of the trial. Diuretic doses do not need to be stable.
 9. Patient meets at least 2 of the following criteria at the Screening Visit:
 - a. Diagnosis of type 2 diabetes mellitus or prediabetes (currently treated **or** hemoglobin A1c ≥ 5.6)
 - b. History of hypertension (on at least 1 antihypertensive medication **or** has current seated blood pressure [BP] $>140/90$ mmHg)
 - c. Body mass index (BMI) >30 kg/m²
 - d. Age ≥ 70 years
 10. Female patient must be postmenopausal (no menses for ≥ 12 consecutive months) or surgically sterile (ie, bilateral oophorectomy, hysterectomy, or tubal sterilization [tie, clip, band, or burn]). Female patients of reproductive potential must agree to completely abstain from heterosexual intercourse; or, if heterosexually active, must agree to use 1 of the following methods of birth control from the date she signs the ICF until 60 days after the final dose of study drug:
 - a. Progesterone implant and/or an intrauterine device (IUD), or
 - b. Combination of 2 highly effective birth control methods (eg, diaphragm with spermicide plus a condom, condom with spermicide plus a diaphragm or cervical cap, hormonal

contraceptive [eg, oral and transdermal patch] combined with a barrier method, partner with vasectomy [conducted ≥ 60 days before the Screening Visit or confirmed via sperm analysis] plus a hormone or barrier method).

11. Male patients who are not surgically sterile by vasectomy (conducted ≥ 60 days before the Screening Visit or confirmed via sperm analysis) must agree to completely abstain from heterosexual intercourse or, if heterosexually active, must agree to use a highly effective birth control method (eg, condom with spermicide; partner IUD; partner diaphragm or cervical cap; partner hormonal contraceptive [including progesterone implant]; or postmenopausal partner [no menses for ≥ 12 consecutive months]) starting from the Screening Visit through 60 days after the final dose of study drug.
12. Patient must agree not to make any major lifestyle (eg, diet, exercise) changes from the Screening Visit through the Follow-up Visit.

EXCLUSION CRITERIA

Patients who meet any of the following criteria will not be eligible to participate in the study:

1. Patient has had acute coronary syndrome or percutaneous coronary intervention within 30 days before Randomization.
2. Patient has had cardiac transplantation or has cardiac transplantation planned during the study.
3. Patient has had coronary artery bypass graft, cardiac mechanical support implantation, or other cardiac surgery in the 3 months before the Screening Visit or planned during the study.
4. Patient has severe chronic obstructive pulmonary disease (COPD) as defined by chronic oxygen dependence. Nighttime oxygen is not exclusionary.
5. Patient had had heart failure hospitalization with discharge within 30 days before the Baseline Visit.
6. Patient has hypertrophic cardiomyopathy (obstructive or nonobstructive), restrictive cardiomyopathy, active myocarditis, constrictive pericarditis, cardiac sarcoidosis, or known amyloid cardiomyopathy.
7. Patient has uncontrolled arrhythmias other than permanent or persistent atrial fibrillation.
8. Patient has history of uncorrected congenital cardiac disease affecting LV function.
9. Patient has evidence of severe chronotropic incompetence, as indicated by a heart rate response $<55\%$ of predicted maximum heart rate ($220 - \text{age}$) per Baseline Visit CPET.
10. Patient has any history of platelet dysfunction, hemophilia, von Willebrand disease, coagulation disorder causing a bleeding diathesis, other bleeding diathesis, or significant, nontraumatic bleeding episodes, such as from a gastrointestinal source.

11. Patient has uncorrected thyroid disease.
12. Patient has severe aortic stenosis or severe mitral regurgitation.
13. Patient has seated systolic BP <110 mmHg at the Screening Visit and on Day 1 before Randomization. For these determinations of eligibility, BP will be the average of 3 measurements obtained at approximately 2-minute intervals after the patient has been sitting quietly for ≥ 5 minutes.
14. Patient has estimated glomerular filtration rate (eGFR) <30 mL/min/1.73m² at the Screening Visit and/or is receiving dialysis.
15. Patient has direct bilirubin >2 times upper limit of normal (\times ULN, as defined by laboratory) or alanine aminotransferase (ALT) or aspartate aminotransferase (AST) >3 \times ULN at the Screening Visit.
16. Patient has received IV inotropic therapy within 30 days before the Screening Visit.
17. Patient is unable to take oral medications.
18. Patient has active or treated malignancies within 12 months of the Screening Visit, except for basal cell carcinoma.
19. Patient has previously received IW-1973, has received any other investigational drug during the 30 days or 5 half-lives of that investigational drug (whichever is longer) before the Screening Visit, is planning to receive another investigational drug at any time during the study, has an active investigational medical device currently implanted, and/or is planning to have an investigational medical device implanted at any time during the study.
20. Patient has comorbid condition with an expected survival less than 6 months.
21. Patient has any medical condition that, in the Investigator's opinion, could lead to difficulty complying with protocol procedures (eg, 6-minute walk test, CPET) or could prohibit completion of the study. Specifically, patients should not be primarily limited in their physical activity by joint, leg, hip or back pain, or gait unsteadiness.
22. Patient has evidence of active hepatitis or human immunodeficiency virus antibody at the Screening Visit.
23. Patient has clinically significant (per Investigator judgment) history of viral or bacterial infection within 4 weeks of the Baseline Visit.
24. Patient has had surgery with general anesthesia in the 6 weeks before the Screening Visit or has scheduled or planned surgery with general anesthesia during the study.
25. Patient has a history of active alcoholism or drug addiction during the 12 months before the Screening Visit and/or has a positive drug screen at the Screening Visit for amphetamines, barbiturates, benzodiazepines, cocaine, opiates, phencyclidine, propoxyphene without a prescription for a medically defined condition.

26. Patient is taking specific inhibitors of phosphodiesterase 5 (PDE5), nonspecific inhibitors of PDE5 (including dipyridamole and theophylline), any supplements for the treatment of erectile dysfunction, riociguat, and/or nitrates or nitric oxide (NO) donors in any form. These medications and supplements are prohibited from 7 days before Randomization through the duration of the study.

Patient is taking strong cytochrome P450 3A (CYP3A) inhibitors, examples of which include azole antifungals, macrolide antibiotics, protease inhibitors, and diltiazem. These medications and excessive grapefruit intake are prohibited 14 days before Randomization through the duration of the trial.

See [Appendix 1](#) for a more detailed list of prohibited medicines and supplements.

27. Patient has a history of clinically significant hypersensitivity or allergy to any of the ingredients contained in the active or placebo drug products.

28. Female patient is pregnant (positive urine pregnancy test) or is breastfeeding. Breastfeeding is not allowed from Screening Visit through 60 days after the final dose of study drug.

29. Female patient who may wish to become pregnant and/or plans to undergo egg donation or egg harvesting for current or future in vitro fertilization during the study and/or within at least 60 days after the final dose of study drug.

30. Male patient unwilling to refrain from sperm donation during the study and for at least 60 days after the final dose of study drug.

31. Patient will not be able to adhere to the trial assessment schedule or, in the clinical judgment of the Investigator, is otherwise not suitable for the trial.

NOTES:

- Patients may be rescreened should they discontinue in the Screening Period due to visit window deviations or other administrative reasons.
- Laboratory values or BPs that are outside the range specified in the protocol may be repeated to confirm eligibility during the Screening Period at the Investigator's discretion after consultation with the Medical Monitor.
- The Screening and Baseline Visits can be combined if the visit occurs within 14 days of Randomization and the patient has fasted for ≥ 8 hours.
- With prior approval by the Medical Monitor, local laboratory results may be used to determine study eligibility. In this instance, patients must have fasted for ≥ 8 hours prior to collection of the laboratory samples and duplicate samples must be drawn—1 set will be used for determination of study eligibility by the local laboratory and the second set will be sent to the Central laboratory for inclusion in the study database. The Randomization Visit can then occur on the next day.

SCHEDULE OF EVENTS

Study Procedure ↓	Screening Period			Treatment Period				FU Period (Day 113 ±7)
	Screening Visit* (Day -45 to -3)	Baseline* Visit (Day -14 to -3)	Randomization Visit (Day 1)	Week 2 Visit (Day 15 ±3)	Week 4 Visit (Day 29 ±3)	Week 8 Visit (Day 57 ±3)	Week 12/ EOT Visit (Day 85 -7/+4)	
ICF signed	X							
Demographics	X							
Medical history	X							
Inclusion/exclusion	X	X	X					
Prior & concomitant medications and procedures	X	X	X	X	X	X	X	X
Physical exam (a)	complete	pre CPET	predose	predose	predose	predose	predose	complete
Vital signs (BP, pulse, RR, & oral temperature) (b)	X	pre CPET	pre: 0 (≤1h) pd: 1,3,4h (±20m)	pre: 0 (≤1h) pd: 1,3,4h (±20m)	pre: 0 (≤1h)	pre: 0 (≤1h)	pre: 0 (≤1h)	X
Weight, height	W, H	W	W	W	W	W	W	W
NYHA classification	X		X			X		X
Hepatitis, HIV screen	X							
Urine drug screen	X							
Urine pregnancy (c)	X	pre CPET	predose	predose	predose	predose	predose	X
Urinalysis sample (d)	X	pre CPET	predose	predose	predose	predose	predose	X
Serum chemistry, CBC, coagulation (d)	X	pre CPET	predose	predose	predose	predose	predose	X
Hemoglobin A1c	X	pre CPET						X
12-lead ECG (e)	X	pre CPET	predose	predose	predose	predose	predose	X
Adverse events	X	X	X	X	X	X	X	X
CPET (f)		X					postdose >1h (or ±3 days) (f)	
6MWT (g)		post CPET >1h					post CPET >1h (g)	post CPET >1h
NT-proBNP sample (d,h)	X (if needed)	pre CPET						
Echocardiography (i)	X (if needed)		X (for baseline)				predose	X

Visit Days → Study Procedure ↓	Screening Period		Treatment Period				FU Period (Day 113 ±7)
	Screening Visit* (Day -45 to -3)	Baseline* Visit (Day -14 to -3)	Randomization Visit (Day 1)	Week 2 Visit (Day 15 ±3)	Week 4 Visit (Day 29 ±3)	Week 8 Visit (Day 57 ±3)	
Fasting plasma glucose & insulin (d)	pre CPET	predose				predose	predose
UACR sample supplies dispensed		X				X	
First-void urine samples (j)			preVisit			X	preVisit
Pharmacokinetic blood samples			predose pd:1,2,4h (±20m)	predose pd:1,2,4h (±20m)	predose pd:1,2,4h (±20m)	predose pd:1,2,4h (±20m)	X
Orthostatic (sitting to standing) pulse, BP (k)		pre: 0 (≤1h) pd: 2,4h (±20m)	pre: 0 (≤1h) pd: 2,4h (±20m)				pre: 0 (≤1h)
Randomization		X					
Study drug dispensed		X	X	X	X		
In-clinic study drug (l)		X	X	X	X	X	
Study drug return			X	X	X	X	
Study completion						X	

6MWT=6-minute walk test; BP=blood pressure; CBC=complete blood count; CPET=cardiopulmonary exercise test; CV=cardiovascular; ECG=electrocardiogram; EOT=end of treatment; [REDACTED] FU=follow-up; h=hour; H=height; HIV=human immunodeficiency virus; ICF=informed consent form; [REDACTED] m=minute(s); NT-proBNP=N-terminal pro B-type natriuretic peptide; NYHA=New York Heart Association; opt=optional; pd=postdose; pre=predose; QD=once daily; [REDACTED]

* Screening and Baseline Visits may be combined if the visit occurs within 14-day period before Randomization and if patient has fasted ≥ 8 h. With prior approval from the Sponsor's Medical Monitor, the Screening and Baseline Visits can be combined and can occur 1 day prior to the Randomization Visit; in these instances, local laboratory values can be used to determine study eligibility, with duplicate samples sent to the Central laboratory for inclusion in the study database. Patients must have fasted for ≥ 8 hours prior to collection of the laboratory samples.

- a. For Treatment Period visits, physical exam may be symptom directed or limited to cardiovascular system at the Investigator's discretion.
- b. For eligibility at the Screening and Randomization Visits, BP will be the average of 3 measurements obtained at approximately 2-m intervals after the patient has been sitting quietly for ≥ 5 m; otherwise, 1 measurement after the patient has been sitting quietly for ≥ 5 m.
- c. For female patients, a pregnancy test (by urine dipstick) must be documented at all visits and confirmed negative before dosing when applicable. Pregnancy tests are not required for female patients who are postmenopausal (no menses for ≥ 12 consecutive months) or surgically sterile (ie, bilateral oophorectomy, hysterectomy, or tubal sterilization [tie, clip, band, or burn]).
- d. Pre CPET and predose samples require ≥ 8 -h fast; fasting not required for the Screening Visit unless combined with Baseline Visit; blood collections after ECG or ≥ 10 m before ECG, when applicable. [REDACTED]
- e. Patients must be supine for ≥ 5 minutes before the ECG recording. ECGs conducted before blood collections or ≥ 10 m after blood collections, when applicable.
- f. CPETs should be performed at the same time of day (± 2 h) and be timed to occur at ≥ 1 h postdose, when applicable. CPET will precede 6MWT by ≥ 1 h, when applicable. The Week 8 CPET can be conducted on a separate day (± 3 days) from the other Week 8 assessments, as dictated by logistical considerations.
- g. When applicable, 6MWT must be performed ≥ 1 h after CPET.
- h. At Screening Visit only if needed for eligibility determination.
- i. Echocardiography may be performed at the Screening Visit to confirm eligibility; if performed at the Screening Visit, it can be used for baseline and does not need to be repeated at the Baseline or Randomization Visit. If not performed at the Screening Visit, echocardiography for baseline may be performed at either the Baseline or Randomization Visit. Echocardiography performed at Baseline and EOT Visits must be before or ≥ 1 h after exercise (CPET, 6MWT).
- j. One patient-collected, first-void urine sample from the morning before or the morning of the scheduled visit. Patients will be supplied with specimen collection supplies at the preceding study visit.
- k. Patient must sit quietly for ≥ 5 m before sitting BP and pulse measurements are taken, and then assume standing position for 2 m (± 1 m) before standing BP and pulse measurements are taken.
- l. Study drug will be administered in the clinic on study visit days after predose assessments. On Day 1, only the morning dose will be administered in clinic. For at home dosing, patients will be instructed to take study drug with water at approximately the same time each day. Patients may take with or without food and, for QD dosing (Week 2 Visit onward), may swallow the 2 tablets together.

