3.6 RESTRICTIONS

3.6.1 Prohibited Medicines and Supplements

The following medicines and supplements are prohibited from 7 days before the Randomization Visit (Day 1) through the duration of the trial:

- Specific inhibitors of phosphodiesterase 5 (PDE5) (including sildenafil and tadalafil)
- Nonspecific inhibitors of PDE5 (including dipyridamole and theophylline)
- Any supplements for the treatment of erectile dysfunction
- Riociguat, or any sGC stimulator
- Nitrates or NO donors in any form

The following medicines and supplements are prohibited from 14 days before the Randomization Visit (Day 1) through the duration of the trial:

- Strong inhibitors of CYP3A; examples include azole antifungals, macrolide antibiotics, protease inhibitors, diltiazem, and concentrated grapefruit supplements

See [Appendix 1](#) for a more detailed list of prohibited medicines and supplements.

Should there be an urgent need for nitrate administration, it should occur in a monitored in-patient setting.

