3.8.5 Vital Signs

Vital signs will include seated BP, pulse, respiratory rate, and oral temperature (°C). All vital signs should be measured after the patient has been sitting quietly for at least 5 minutes. For the Screening and Randomization Visits, BPs for eligibility will be the average of 3 measurements obtained at approximately 2-minute intervals.

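### Exclusion 13 joins its two systolic pressure checks with 'and', so read literally it does not exclude a patient who is below 110 mmHg only on Day 1 before Randomization

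*Protocol*

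**What the plan says.** The exclusion list makes a patient ineligible if any one criterion is met, so a criterion must itself be true before it excludes anyone. Exclusion 13 is: "Patient has seated systolic BP <110 mmHg at the Screening Visit and on Day 1 before Randomization". Its second sentence gives the measurement rule: "For these determinations of eligibility, BP will be the average of 3 measurements".

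Three other places bear on it:

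- Schedule of Events, footnote b (repeated in the SAP's Table 2): "For eligibility at the Screening and Randomization Visits, BP will be the average of 3 measurements".
- Protocol 3.8.5: "For the Screening and Randomization Visits, BPs for eligibility will be the average of 3 measurements obtained at approximately 2-minute intervals".
- The notes after the exclusion criteria: "Laboratory values or BPs that are outside the range specified in the protocol may be repeated to confirm eligibility during the Screening Period". This is at the Investigator's discretion, after consulting the Medical Monitor.

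The Schedule of Events also marks the inclusion/exclusion check at Screening, Baseline and Randomization. The other blood pressure criterion, Inclusion 9b, is tied to Screening: "Patient meets at least 2 of the following criteria at the Screening Visit".

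**The concern.** Joined by *and*, the criterion is true only when both averages are below 110 mmHg. A patient who passes at Screening therefore cannot fail on Day 1, whatever the pressure is just before the first dose. Yet the Day 1 reading is the one closest to dosing. Screening may be up to 45 days earlier, and Inclusion 8 does not require diuretic doses to be stable.

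Exclusion 13 is the only numeric lower limit on blood pressure before dosing in the visible text. Hypotension is a named risk. Table 5 in Protocol 3.7 makes symptomatic hypotension a trigger for DMC review, Protocol 3.7.1 makes it a ground for stopping an individual's dosing, and SAP 6.9.2.2 treats it as a possible class effect. What is at stake is patient safety at the first dose, and whether all sites apply the same eligibility rule.

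**Working it through.** **Truth table.** Let S mean the Screening average is below 110 mmHg, and D the Day 1 average before Randomization is below 110 mmHg.

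| S | D | As written (S and D) | Day 1 limit alone (D) | Either visit (S or D) |
|---|---|---|---|---|
| yes | yes | excluded | excluded | excluded |
| no | yes | **eligible** | excluded | excluded |
| yes | no | eligible | eligible | excluded |
| no | no | eligible | eligible | eligible |

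The second row is the gap. Patients in the third row are at or above 110 mmHg before the dose.

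**What the text suggests was meant.** The criterion's second sentence refers to eligibility determinations in the plural. Footnote b and Protocol 3.8.5 ask for the eligibility average at both visits for everyone, not only for those low at Screening. Inclusion 9b uses Screening, so Exclusion 13 is the only criterion that uses the Day 1 average. All this points to two separate checks. Against it, Exclusion 14 uses *and/or* where either condition is enough, so that wording was available and was not used in Exclusion 13.

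**Illustrative size.** The plan states no figure to reproduce, and neither document gives a mean, SD or between-visit correlation for systolic pressure. The inputs below are assumptions: bivariate normal, same mean and SD at both visits, mean 125, 130 or 135 mmHg, SD 12, 15 or 18, correlation 0.4 to 0.8.

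- p = P(below 110 at a given visit) = Φ((110 − mean)/SD)
- b = P(below 110 at both visits)
- d = p − b = P(low on Day 1 only)
- Expected number among 184 randomised under the literal rule = 184 × d / (1 − b)

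Central case (mean 130, SD 15, correlation 0.6): p = Φ(−1.333) = 0.0912; b = 0.0345; d = 0.0567; 184 × 0.0567 / 0.9655 = 10.8.

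Lowest on the grid (135, 12, 0.8): 2.0. Highest (125, 18, 0.4): 24.9.

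**Share on active drug.** The sample size section (Protocol 5.2) assumes that 10% of patients were randomised to 10 or 20 mg, which is 18.4 of 184. The other 165.6 split 1:1, giving 82.8 on 40 mg. Active total = 18.4 + 82.8 = 101.2, or 55%. Applying 0.55 gives about 6 in the central case (10.8 × 0.55 = 5.9) and about 1 to 14 over the grid (2.0 × 0.55 = 1.1; 24.9 × 0.55 = 13.7).

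**How low they are.** In the central case about 54% of the Day-1-only patients lie at 105 to 110 mmHg, about 82% at 100 to 110, and about 2% below 90 (roughly 0.2 of 184). At the highest corner about 36% are below 100.

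**Screen failures on this criterion, before repeat readings.**

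| Rule | Probability | Central case | Range over grid |
|---|---|---|---|
| As written | b | 3.5% | 0.2–13% |
| Day 1 alone | p | 9.1% | 2–20% |
| Either visit | 2p − b | 14.8% | 3–33% |

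**The case against.** The best defence is that *and* simply lists the visits at which the check is made. Eligibility is assessed visit by visit, and under the strict reading a low Screening value could never fail anyone at Screening, which would be odd. Many sites may already apply the protective reading. This stands as evidence of intent, but it does not settle the rule: the literal text permits enrolment of a patient low only on Day 1, and sites that read it differently would apply different criteria.

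A second defence is that the sponsor wanted confirmed low pressure, with Day 1 clearing or confirming a low Screening value. That fits poorly with averages required unconditionally at both visits and with a repeat-reading note that already provides confirmation. It would also leave the Day-1-only patient eligible.

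Third, other safeguards exist. Exclusion 31 lets the Investigator refuse anyone who, "in the clinical judgment of the Investigator, is otherwise not suitable for the trial". "Nitrates or NO donors in any form" are banned from 7 days before Randomization, as are PDE5 inhibitors and riociguat. Day 1 has predose vital signs and orthostatic readings before and after the dose, with a stay of about 4 hours. Dosing is split for two weeks and can be halved. These reduce the risk and that part of the objection stands, but none sets a numeric limit before dosing.

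A reader might infer from the calculation that about 11 hypotensive patients would be dosed. The documents do not support that. The blood pressure parameters are assumed, the count includes placebo patients, it needs literal reading at every site with no use of Exclusion 31, and most of those counted are only just below the cut-off. The assumed grid is not a bound either: at mean 140, SD 15 and correlation 0.6 the same model gives about 3.

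**Conclusion.** The point holds as a minor safety matter in an operative eligibility rule. As written, Exclusion 13 does not exclude a patient who is below 110 mmHg only on Day 1, and nothing in the protocol or SAP closes that gap. This conclusion rests on the text alone. The figures of 2 to 25 of 184 randomised, and 1 to 14 on active drug, rest wholly on the assumptions above and only illustrate scale.

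Two stronger readings should be resisted. The first is that *or* was certainly intended: the context favours separate checks, but no sentence says that a low value at either visit excludes. The second is that the efficacy result is affected: nothing here bears on power or the primary analysis, and SAP 6.2 does not list Exclusion 13 among the key criteria for major deviations.

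**What to change.** Make the Day 1 limit unconditional by rewording Exclusion 13 so that a seated systolic average below 110 mmHg on Day 1, before Randomization, excludes by itself. This is the part needed for safety. If the sponsor confirms that a low value at either visit was meant to exclude, replace *and* with *or* instead. If confirmed low pressure was intended, the protocol should say so openly and still set a Day 1 limit. Keep the three-reading average and the repeat-reading note in every case. With *or*, footnote b and Protocol 3.8.5 need no change.

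The cost is a short eligibility amendment with IRB/IEC approval (Protocol 6.1), made after some patients have already been randomised. No new measurement is needed. Extra screen failures arise only where sites have been applying the literal text: in the central case the share failing rises from 3.5% to 9.1% with a Day 1 limit alone, or to 14.8% with *or*. The *or* version costs more because it also turns away patients low only at Screening.
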